### 8.3.3 Storage period of records

Trial site:

The trial site must retain the source and essential documents (including ISF) according to the local requirements valid at the time of the end of the trial.

Sponsor:

The sponsor must retain the essential documents according to the sponsor's SOPs.

## 8.4 EXPEDITED REPORTING OF ADVERSE EVENTS

BI is responsible to fulfil their legal and regulatory reporting obligation in accordance with regulatory requirements.

## 8.5 STATEMENT OF CONFIDENTIALITY AND SUBJECT PRIVACY

Individual subject data obtained as a result of this trial is considered confidential and disclosure to third parties is prohibited with the exceptions noted in Section [8.7](#).

Data protection and data security measures are implemented for the collection, storage and processing of patient data in accordance with the principles 6 and 12 of the WHO GCP handbook.

Personalised treatment data may be given to the subject's personal physician or to other appropriate medical personnel responsible for the subject's welfare. Data generated at the site as a result of the trial need to be available for inspection on request by the participating physicians, the sponsor's representatives, by the IRB / IEC and the regulatory authorities.

### 8.5.1 Collection, storage and future use of biological samples and corresponding data

Measures are in place to comply with the applicable rules for the collection, storage and future use of biological samples and clinical data, in particular

- Sample and data usage has to be in accordance with the informed consent
- The BI-internal facilities storing biological samples from clinical trial participants as well as the external storage facility are qualified for the storage of biological samples collected in clinical trials.
- An appropriate sample and data management system, incl. audit trail for clinical data and samples to identify and destroy such samples according to ICF is in place
- A fit for the purpose documentation (biomarker proposal, analysis plan and report) ensures compliant usage
- A fit for purpose approach will be used for assay/equipment validation depending on the intended use of the biomarker data

Samples and/or data may be transferred to third parties and other countries as specified in the ICF.

## 8.6 TRIAL MILESTONES

The **start of the trial** is defined as the date of the enrolment of the first subject in the trial.

The **end of the trial** is defined as the ‘date of the last visit of the last subject in whole trial’ (‘Last Subject Completed’) or ‘end date of the last open AE’ or ‘date of the last follow-up test’ or ‘date of an AE has been decided as sufficiently followed-up’, whichever is latest.

**Early termination of the trial** is defined as the premature termination of the trial for any reason before the end of the trial as specified in this protocol.

**Temporary halt of the trial** is defined as any unplanned interruption of the trial by the sponsor with the intention to resume it.

**Suspension of the trial** is defined as an interruption of the trial based on a Health Authority request.

The EC/competent authority in each participating EU member state will be notified about the trial milestones according to the laws of each member state.

A final report of the clinical trial data will be written only after all subjects have completed the trial in all countries (EU or non-EU), so that all data can be incorporated and considered in the report.

The sponsor will submit to the EU database a summary of the final trial results within one year from the end of a clinical trial as a whole, regardless of the country of the last patient (EU or non-EU).

## 8.7 ADMINISTRATIVE STRUCTURE OF THE TRIAL

The trial is sponsored by Boehringer Ingelheim (BI).

The trial will be conducted at the [REDACTED] of [REDACTED], under the supervision of the Principal Investigator. Relevant documentation on the participating (Principal) Investigators (e.g. their curricula vitae) will be filed in the ISF.

BI has appointed a Clinical Trial Leader, responsible for coordinating all required trial activities, in order to

- Manage the trial in accordance with applicable regulations and internal SOPs
- Direct the clinical trial team in the preparation, conduct, and reporting of the trial
- Ensure appropriate training and information of Clinical Trial Managers, Clinical Research Associates, and investigators of participating trial sites

The trial medication BI 1323495 will be provided by the [REDACTED]. Rosuvastatin and dabigatran supplies will be obtained from a public pharmacy in Germany.

Safety laboratory tests will be performed by the local laboratory of the trial site ([REDACTED]).

Analyses of BI 1323495, rosuvastatin and dabigatran concentrations in plasma will be done by [REDACTED].

On-site monitoring will be done by BI or a contract research organisation appointed by BI.

Data management and statistical evaluation will be done by BI or a contract research organisation appointed by BI according to BI SOPs.

Tasks and functions assigned in order to organise, manage, and evaluate the trial are defined according to BI SOPs. A list of responsible persons and relevant local information can be found in the ISF.

## **10. APPENDICES**

Not applicable.

## 11. DESCRIPTION OF GLOBAL AMENDMENT(S)

### 11.1 GLOBAL AMENDMENT 1

Date of amendment		22 June 2020
EudraCT number		2019-004245-33
EU number		
BI Trial number		1405-0015
BI Investigational Medicinal Product(s)		BI 1323495
Title of protocol		Relative bioavailability of rosuvastatin (Part 1) and dabigatran (Part 2) given alone and together with BI 1323495 in healthy male subjects (open, single-dose, randomised, two-period crossover design in each trial part)
To be implemented only after approval of the IRB / IEC / Competent Authorities		
To be implemented immediately in order to eliminate hazard – IRB / IEC / Competent Authority to be notified of change with request for approval		
Can be implemented without IRB / IEC / Competent Authority approval as changes involve logistical or administrative aspects only		
Section to be changed		1) Flow Chart Part 1 2) Section 3.3.3 Exclusion Criteria 3) Section 8.1 Trial Approval, Subject Information, Informed Consent
Description of change		1) Typo corrected 2) Exclusion criterion no. 27 introduced (exclude subjects with positive SARS-CoV-2 testing) 3) Specified that separate informed consent for SARS-CoV-2 testing will be used.
Rationale for change		Additional measures for risk reduction during COVID-19 pandemic described

2. LIST OF ABBREVIATIONS

See Medicine Glossary:

Website: glossary

Term	Definition / description
ALT	Alanine transaminase
AST	Aspartate transaminase
AUC0-tz	Area under the concentration-time curve of the analyte in plasma over the time interval from 0 to the last quantifiable data point
AUC0-∞	Area under the concentration-time curve of the analyte in plasma over the time interval from 0 extrapolated to infinity
BMI	Body mass index
CARE	Clinical data Analysis and Reporting Environment
CI	Confidence interval
Cmax	Maximum measured concentration of the analyte in plasma
CV	Arithmetic coefficient of variation
DBLM	Database lock meeting
DILI	Drug induced liver injury
gCV	Geometric coefficient of variation
gMean	Geometric mean
LLT	Lower level term
IQRMP	Integrated Quality and Risk Management Plan
λ_z	Terminal rate constant of the analyte in plasma
Max	Maximum
MedDRA	Medical Dictionary for Regulatory Activities
Min	Minimum
N	Number of non-missing observations
P10	10th percentile
P90	90th percentile
po	Orally
PKS	Pharmacokinetic parameter analysis set
Q1	1st quartile
Q3	3rd quartile

Term	Definition / description
qd	Once daily
R	Reference treatment
RAGe	Report Appendix Generator system
REP	Residual effect period
SD	Standard deviation
SOC	System organ class
T	Test treatment
TS	Treated set
ULN	Upper limit of normal
WHO-DD	World Health Organization Drug Dictionary

3. INTRODUCTION

As per ICH E9 (1) the purpose of this document is to provide a more technical and detailed elaboration of the principal features of the analysis described in the protocol, and to include detailed procedures for executing the statistical analysis of the primary and secondary variables and other data.

This Trial statistical analysis plan (TSAP) assumes familiarity with the Clinical Trial Protocol (CTP). In particular, the TSAP is based on the planned analysis specification as written in CTP Section 7 “Statistical Methods and Determination of Sample Size”. Therefore, TSAP readers may consult the CTP for more background information on the study, e.g., on study objectives, study design and population, treatments, definition of measurements and variables, planning of sample size, randomisation.

Study data (including data entered in the RAVE EDC system and external data provided by suppliers) will be stored in a Clinical Data Repository (CDR).

Pharmacokinetic (PK) parameters will be calculated using Phoenix WinNonlin™ software (version 6.3 or higher, Certara USA Inc., Princeton, NJ, USA).

The statistical analyses will be performed within the validated working environment CARE, including SAS™ (current Version 9.4, by SAS Institute Inc., Cary, NC, USA), and a number of SAS™-based tools (e.g., macros for the analyses of AE data or laboratory data; Report Appendix Generator system (RAGe) for compilation/formatting of the CTR appendices).

4. CHANGES IN THE PLANNED ANALYSIS OF THE STUDY

All analyses as planned in the CTP will be performed and are described in more detail in this TSAP.

5. ENDPOINTS

5.1 PRIMARY ENDPOINTS

Section 2.1.2 of the CTP:

The following pharmacokinetic parameters will be determined for rosuvastatin (Part 1) and dabigatran (Part 2):

- $AUC_{0-\infty}$ (area under the concentration-time curve of the analyte in plasma over the time interval from 0 extrapolated to infinity)
- C_{max} (maximum measured concentration of the analyte in plasma)

5.2 SECONDARY ENDPOINTS

5.2.1 Key secondary endpoints

[figure not shown]
This section is not applicable as no key secondary endpoints have been defined in the CTP.

[figure not shown]
5.2.2 Secondary endpoint

Section 2.1.3 of the CTP:

The following pharmacokinetic parameter will be determined for rosuvastatin (Part 1) and dabigatran (Part 2):

- AUC_{0-tz} (area under the concentration-time curve of the analyte in plasma over the time interval from 0 to the last quantifiable data point)

6. GENERAL ANALYSIS DEFINITIONS

6.1 TREATMENTS

For basic study information on investigational products, assignment of treatment sequences and selection of doses, please see CTP, Sections 3 and 4.

The study consists of 2 trial parts, Part 1 with rosuvastatin and Part 2 with dabigatran. It is planned that within each part of the study, 14 healthy male subjects will enter. Each part follows an open-label, randomized, two-period, two-way crossover design in order to compare the test (B, D) and reference (A, C) treatments as defined in Table 6.1: 1 below.

Table 6.1: 1 Treatments and labels used in the analysis

Treatment	Short label
Part 1	
A Rosuvastatin, 10 mg tablet, qd	Rosu
B BI 1323495, 6*50 mg tab + Rosuvastatin, 10 mg tab, qd	BI+Rosu
Part 2	
C Dabigatran etexilate, 75 mg capsule, qd	Dabi
D BI 1323495, 6*50 mg tab + Dabigatran etex, 75 mg caps, qd	BI+Dabi

Section 1.2.4 of CTP:

The Residual Effect Period (REP) of BI 1323495, rosuvastatin, and dabigatran, i.e. the period after the last dose with measurable drug levels and/or pharmacodynamic effects still likely to be present, will be defined as 7 days for each of the 3 products.

The following study phases in Part 1 and Part 2 will be defined for the analysis of adverse events (AEs):

- **Screening** (ranging from 0:00 h on day of informed consent until first administration of study medication in treatment period 1)
- **On treatment** (ranging from the time of administration of test or reference treatment until administration time of next study drug dose or until 0:00 h on day 7 after time of administration, whatever occurs first)

→ labelled **Rosu, BI+Rosu, Dabi, BI+Dabi**

- **Follow-up (F/U)** (ranging from 0:00 h on day 7 after the time of administration of test or reference treatment until administration time of next study drug dose or until 0:00 h on day after trial termination date, whatever occurs first)

→ labelled **F/U Rosu, F/U BI+Rosu, F/U Dabi, F/U BI+Dabi**

Section 7.3.4 of the CTP: *Note that AEs occurring after the last per protocol contact but entered before final database lock will be reported to Pharmacovigilance only and will not be captured in the trial database.*

The following AE displays will be provided in the report:

Section 15.3 and Appendix 16.1.13.1.8 (for ClinicalTrials.gov and EudraCT only) of the CTR displays:

In these displays, the on-treatment phase will be analysed (labelled with the name of the study treatment (short label)). Screening and Follow up phases will not be included in this analysis. The following totals will be provided in addition:

For Section 15.3:

- a total over all on treatment phases in study Part 1 (“**Total - Part 1**”)
- a total over all on treatment phases in study Part 2 (“**Total - Part 2**”)

For ClinicalTrials.gov and EudraCT only:

- a total over all on treatment phases included in this analysis (“**Total**”)

In Section 15.4 and Appendix 16.2 (Listings) of the CTR displays, screening and follow-up periods will be included and no totals will be provided.

Tables of vital signs and laboratory values will present results by the above mentioned on treatment phases.

For detailed information on the handling of the treatments refer to Technical TSAP ADS (analysis data set) plan and Analysis Data Reviewers guide.

In outputs for ClinicalTrials.gov and EudraCT both study parts will be combined.

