#### 1.2.4 Residual Effect Period

The Residual Effect Period (REP) of BI 1323495, rosuvastatin, and dabigatran, i.e. the period after the last dose with measurable drug levels and/or pharmacodynamic effects still likely to be present, will be defined as 7 days for each of the 3 products.

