#### 7.3.4 Safety analyses

Safety will be analysed based on the assessments described in Section [2.2.2.4](#). All treated subjects (TS, refer to Section [7.2](#)) will be included in the safety analysis. Safety analyses will be descriptive in nature and based on BI standards. No hypothesis testing is planned.

For all analyses, the treatment actually administered (= treatment at onset) to the subject will be used (any deviations from the randomised treatment will be discussed in the minutes of the Report Planning Meeting).

Treatments will be compared in a descriptive way. Tabulations of frequencies/proportions will be used to evaluate categorical (qualitative) data, and tabulations of descriptive statistics will be used to analyse continuous (quantitative) data.

Measurements (such as ECG, vital signs, or laboratory parameters) or AEs will be assigned to treatments (see Section [4.1](#)) based on the actual treatment at the planned time of the measurement or on the recorded time of AE onset (concept of treatment emergent AEs). Therefore, measurements planned or AEs recorded prior to first intake of trial medication will be assigned to the screening period, those between first trial medication intake and end of REP (see Section [1.2.4](#)) will be assigned to the treatment period. Events occurring after the REP but prior to next intake or end of trial termination date will be assigned to 'follow-up'. In case of two or more treatments, the follow-up will be summarized according to the previous treatment. These assignments including the corresponding time intervals will be defined in detail in the TSAP. Note that AEs occurring after the last per protocol contact but entered before final database lock will be reported to Pharmacovigilance only and will not be captured in the trial database.

Additionally, further treatment intervals (analysing treatments) may be defined in the TSAP in order to provide summary statistics for time intervals, such as combined treatments, on-treatment totals, or periods without treatment effects (such as screening and follow-up intervals).

Adverse events will be coded using the Medical Dictionary for Regulatory Activities (MedDRA). Frequency, severity, and causal relationship of AEs will be tabulated by treatment, system organ class, and preferred term. SAEs, AESIs (see Section [5.2.6.1](#)), and other significant AEs (according to ICH E3) will be listed separately.

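### Does the midnight cut in SAP 6.1 start adverse-event follow-up before the 7-day residual effect period has ended?

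*SAP*

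**What the plan says.** Protocol 1.2.4 says that the REP "will be defined as 7 days for each of the 3 products", running from the last dose; SAP 6.1 repeats this. Protocol 7.3.4 allocates AEs by onset ("or on the recorded time of AE onset"). Events before the first intake belong to screening, and "those between first trial medication intake and end of REP" belong to treatment. "Events occurring after the REP but prior to next intake or end of trial termination date will be assigned to" follow-up. The same paragraph adds: "These assignments including the corresponding time intervals will be defined in detail in the TSAP".

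SAP 6.1 then sets three phases:

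- Screening: "ranging from 0:00 h on day of informed consent until first administration of study medication in treatment period 1".
- On treatment: from the time of administration until the next dose "or until 0:00 h on day 7 after time of administration, whatever occurs first".
- Follow-up: "ranging from 0:00 h on day 7 after the time of administration of test or reference treatment", until the next dose or the day after trial termination.

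SAP 6.1 restricts the Section 15.3 tables and the ClinicalTrials.gov/EudraCT displays to the on-treatment phases. Screening and follow-up events appear in Section 15.4 and Appendix 16.2, with follow-up labelled by the preceding treatment. SAP Section 4 declares no change from the protocol.

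**The concern.** The on-treatment phase opens at a clock time, the moment of dosing, but closes at a midnight. If the 7 days run from the dose, the REP ends at about 08:00 on the seventh day after dosing, while the SAP closes the phase at 0:00 h that day. An AE with onset in between would be on treatment by Protocol 7.3.4 and follow-up by SAP 6.1.

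Read that way, the shift goes in one direction: it can only take events out of the on-treatment tables and registry totals. With 14 subjects per part, one relabelled subject is 1/14 = 7.1% of a treatment column. Nor is the mismatch declared in SAP Section 4.

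**Working it through.** **Inputs.** Dosing at about 08:00 on Day 1, end-of-trial window from Day 8 (both flow charts). REP 7 days (Protocol 1.2.4). Fourteen subjects per part. Treatment-emergent AEs in 5 of 12 and 6 of 14 subjects in two earlier trials (Protocol 1.2.1).

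**Step 1: where the cut falls.** Read day 7 after administration as the dosing date + 7, which is study Day 8. Elapsed time at 0:00 h is 7 × 24 − (clock hour of dosing).

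| Dosing time | SAP cut (h after dose) | Gap to 168 h | Share of 168 h |
|---|---|---|---|
| 07:00 | 161 | 7 h | 4.2% |
| 08:00 | 160 | 8 h | 4.8% |
| 10:00 | 158 | 10 h | 6.0% |

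The 07:00 and 10:00 rows are an assumed range around the planned time.

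**Step 2: does any count reproduce the 7-day REP?**

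- Hours from an 08:00 dose to the SAP cut: 160 h against 168 h. No.
- Calendar dates, dosing date first: Days 1 to 7 end at 0:00 h on Day 8, the SAP cut. Seven dates, gap 0 h. Yes.
- Day 7 taken as study Day 7: 136 h, six dates. No; 32 h short of 168 h and one date short.
- End of the seventh day after dosing: 184 h, eight dates. No; 16 h over.

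The calendar-date count is the only one that returns 7 days. It makes no difference whether the dosing date is called day 0 or Day 1: days 0 to 6 and Days 1 to 7 are the same seven dates. The clock-time start does not contradict this count either, because an on-treatment phase cannot begin before the dose however its end is counted.

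**Step 3: how many events could be relabelled, if the REP is read as 168 h?** Assume one AE per affected subject, giving 14 × 5/12 = 5.83 or 14 × 6/14 = 6 AEs per part.

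- Onsets even over the REP: 5.83 × 8/168 = 0.28; 6 × 8/168 = 0.29.
- Onsets exponential with mean m, truncated at 168 h. The share falling in 160 to 168 h is (e^(−160/m) − e^(−168/m)) / (1 − e^(−168/m)).
  - m = 48 h: share 0.0056, so about 0.03 AEs.
  - m = 24 h: share 0.00036, so about 0.002 AEs.

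The onset shapes are assumptions. The even spread is unfavourable for a single dose: by 160 h, 160/19 = 8.4 rosuvastatin half-lives have passed, and 160/11 = 14.5 for dabigatran, using the half-lives in Protocol 1.2.2 and 1.2.3 (the latter from elderly subjects). No half-life for BI 1323495 is visible. The 6/14 rate comes from a trial with multiple-dose itraconazole and carries over less well.

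**Step 4: would another cut be better?** A cut at administration time + 168 h needs an onset time. Protocol 5.2.6.2.1 asks for it, but Protocol 8.3.1 makes only the onset date mandatory. The standard cited in SAP 6.6 is described as covering missing or incomplete AE dates; its contents are not in the documents, so whether it settles missing times is unknown. The first midnight at or after 168 h is 184 h: 16 h away, twice the present gap, though on the inclusive side.

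**The case for a change.** The best case for a change is that the window is not empty of scheduled activity. If the two doses are exactly 7 days apart, admission for period 2 is at about 06:00, or 166 h after the first dose, and AE questioning, vital signs, ECG and laboratory tests are done within the 3 h before dosing. After period 2, the end-of-trial window opens on that same calendar date. Findings could therefore cluster in the 8 h, and the smooth onset patterns in the working do not model this, so 0.29 is not an upper bound. The count is also unstated, and a programmer who took day 7 to be study Day 7 would cut at 136 h.

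The clustering point stands as a limit on the estimate. It does not change the consequence: such an event is still reported in Section 15.4 and the listings, under the treatment that preceded it. The misreading risk is slight, because a cut at 136 h fails to give 7 days under either an hour count or a date count. SAP 6.1 also refers the reader to a technical analysis-dataset plan for treatment handling; that plan is not available here and may or may not state the count.

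The complaint about SAP Section 4 does not stand. Setting an interval that Protocol 7.3.4 hands to the SAP is added detail, not a departure from the protocol.

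**Conclusion.** The arithmetic behind the concern is right: 160 h against 168 h for an 08:00 dose. It becomes a discrepancy only once 7 days is converted to hours from the dose, and neither document does that. Counted as calendar dates from the dosing date, which fits the Day 1 and Day 8 numbering and the other midnight boundaries in SAP 6.1, the on-treatment phase and the REP agree exactly. This is an unstated but sensible convention in an area that the protocol leaves to the SAP.

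Followed as written, the plan gives sound descriptive safety results. Even on the hour-based reading, the expected effect is about 0.002 to 0.29 relabelled AEs per part, given one AE per affected subject, the earlier trials' rates and the assumed onset patterns. No event is lost from the report, there is no hypothesis test on safety, and no pharmacokinetic endpoint is affected. The alternatives have drawbacks of their own, so moving the cut brings no real gain. A sentence saying how the seven days are counted is optional.

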4. If several actions are indicated at the same time, the intake of meals will be the last action.
5. Letters A, B, and C define different sets of safety laboratory examinations (for details refer to Section 5.2.3)
6. At the end of trial visit the EoTrial examination includes physical examination, vital signs, ECG, safety laboratory (including faecal occult blood test), recording of AEs and concomitant therapies.
7. AEs and concomitant therapies will be recorded throughout the trial, but will be specifically asked for at the times indicated in the Flow Chart above.
8. Period with administration of test treatment (dabigatran + BI 1323495) only

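### AEs with onset in follow-up, including at the scheduled end-of-trial visit, are listed but not counted in the CTR Section 15.3 displays or registry outputs, although the protocol says follow-up will be summarised by previous treatment

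*SAP*

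**What the plan says.** SAP Section 6.1 names the displays concerned as "Section 15.3 and Appendix 16.1.13.1.8 (for ClinicalTrials.gov and EudraCT only) of the CTR displays". For them it states "In these displays, the on-treatment phase will be analysed" and "Screening and Follow up phases will not be included in this analysis". The totals for these displays also run over on-treatment phases only.

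The same section defines four follow-up phases, one for each preceding treatment (F/U Rosu, F/U BI+Rosu, F/U Dabi, F/U BI+Dabi), each "ranging from 0:00 h on day 7 after the time of administration of test or reference treatment" up to the next dose or the day after trial termination. Their stated place in the report is: "In Section 15.4 and Appendix 16.2 (Listings) of the CTR displays, screening and follow-up periods will be included and no totals will be provided".

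Protocol Section 7.3.4 assigns events after the residual effect period (REP) to follow-up and adds: "In case of two or more treatments, the follow-up will be summarized according to the previous treatment". SAP Section 4 states: "All analyses as planned in the CTP will be performed and are described in more detail in this TSAP".

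Both protocol flow charts put the end-of-trial examination on Day 8 to 15. It covers physical examination, vital signs, ECG, safety laboratory and AE recording.

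**The concern.** The protocol announces a summary of follow-up by previous treatment. The SAP sets up the phases needed for it, specifies no frequency display that uses them, and reports no departure from the protocol.

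What is at stake is how a zero is read. The end-of-trial examination is the last scheduled safety check after dosing. If a finding there has its onset recorded at that visit, it is absent from the Section 15.3 counts and from the registry SAE output. A reader of either could take no event in the tables to mean no event in the trial. The point concerns AE, SAE and AESI counts only. It does not touch the pharmacokinetic endpoints.

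**Working it through.** The plan gives no figure to reproduce. The check is clock arithmetic on the documents' own times, followed by a check of the laboratory panels.

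**Inputs**
- Dosing at about 08:00 on Day 1 (protocol flow charts).
- REP of 7 days (protocol Section 1.2.4): 7 × 24 = 168 h.
- On-treatment ends at the next dose or at 0:00 h on day 7 after administration, whichever comes first (SAP Section 6.1).
- End-of-trial examination on Day 8 to 15 (flow charts), taken here as counted from Day 1 of Period 2.
- Wash-out of at least 7 days (protocol Section 3.1).
- 14 subjects planned per part (protocol Section 7.7).

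**Where on-treatment ends**
- If day 7 means dosing date + 7 (Day 8, 0:00 h): 7 × 24 − 8 = 160 h, which is 168 − 160 = 8 h short of the REP.
- If it means study Day 7: 6 × 24 − 8 = 136 h, which is 168 − 136 = 32 h short.

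**Where the end-of-trial visit falls**
- Day 8 begins at 160 h. Under either reading, every scheduled visit on Day 8 to 15 lies in follow-up.
- Day 15 ends at 15 × 24 − 8 = 352 h. With a visit on Day 15, follow-up covers 352 − 160 = 192 h (192/352 = 55%) under the first reading, or 352 − 136 = 216 h (216/352 = 61%) under the second.

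**Effect of the cut-off itself**
- Protocol Section 7.3.4 assigns events up to the end of the REP to the treatment period. On the first reading, an AE with onset between 160 h and 168 h (0:00 to 08:00 on Day 8) is on treatment under the protocol and uncounted follow-up under the SAP.
- With a wash-out of exactly 7 days, this window also contains the pre-dose procedures of Period 2, which are done in the 3 h before dosing (168 − 3 = 165 h to 168 h).

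**Which AESI findings depend on the end-of-trial visit**
- The first hepatic-injury criterion (protocol Section 5.2.6.1.4) needs raised AST and/or ALT together with raised total bilirubin in the same blood sample.
- Table 5.2.3: 1 includes AST and ALT in panels A, B and C, but total bilirubin only in A (screening) and C (end of trial). Panel B, used in the treatment periods, omits it.
- In completers, scheduled post-dose samples can therefore meet this criterion only at the end-of-trial visit. The second criterion, aminotransferases at least 10-fold ULN, can be met from panel B.

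**Size of one event**
- One subject for one treatment: 1/14 = 7.1%. Both parts are combined in the registry outputs, so one subject in that total is 1/28 = 3.6%.

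**The case against.** The strongest reply is that the protocol does not require what the SAP leaves out. Section 7.3.4 itself separates follow-up from the treatment period and leaves the assignments and intervals to the SAP. It says further intervals, follow-up among them, may be defined for summary statistics. It asks only that SAEs and AESIs be listed separately, and sets no rule for registry outputs. The SAP labels follow-up by previous treatment and lists it. Restricting the main comparison to treatment-emergent events is a normal choice in a single-dose trial.

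Much of this stands. On-treatment should remain the main comparison, and the wording on summarising follow-up is open to some interpretation. But leaving intervals to the SAP does not obviously cover omitting the summary, and the SAP neither specifies one nor declares a change.

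Several stronger readings are tempting and are not supported:
- **That these events go unreported.** They appear in Section 15.4 and Appendix 16.2. Whether Section 15.4 also holds frequencies is not stated, and the sponsor's display standards are not available here.
- **That anything first found at the end-of-trial visit is uncounted.** Phase follows recorded onset, not detection. An event with an earlier on-treatment onset is counted. So could be one found at an early-discontinuation examination (protocol Section 3.3.4), which can fall within the on-treatment phase.
- **That a positive occult blood test can never be counted.** In Part 2 the flow chart says "At the end of trial visit the EoTrial examination includes physical examination, vital signs, ECG, safety laboratory (including faecal occult blood test"), but a laboratory finding becomes an AE only if judged clinically relevant (protocol Section 5.2.6.1.1). The onset and early-discontinuation limits apply here too.
- **That a registry entry of no AESI would mislead.** SAP Section 7.8.1 plans EudraCT entries for AEs per arm, non-serious AEs and serious AEs. No AESI registry output is described.

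**Conclusion.** The point holds and should be addressed. AEs with onset in follow-up are excluded from Section 15.3 and the registry outputs. No follow-up frequency summary is specified, although the protocol says follow-up will be summarised, and no change is declared. For completers this takes in every event with onset recorded at the scheduled end-of-trial visit, the only scheduled post-dose point at which the combined transaminase/bilirubin criterion can be met. The mismatch with the REP adds a window of 8 h (32 h on the other reading) in which the two documents assign the same event to different phases.

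How many events would be affected cannot be derived from the documents. The 7.1% and 3.6% are the weight of one subject, assuming all 14 planned subjects per part receive both treatments. The timing assumes an 08:00 dose. The conclusion that the end-of-trial visit lies in follow-up does not depend on which reading of day 7 is used.

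**What to change.** 1. In SAP Section 6.1, add the F/U columns already defined to the Section 15.3 tables, or add one separate follow-up table by previous treatment, covering all AEs, drug-related AEs, SAEs and AESIs. Keep on-treatment as the main comparison and as the basis of the totals.
2. In the registry SAE output, show SAEs with onset in follow-up as separate follow-up counts by previous treatment. Do not merge them into the on-treatment counts, because protocol Section 7.3.4 keeps the two phases apart.
3. Reconcile the 0:00 h cut-off with the 7-day REP, and state which calendar day is meant by day 7 after administration.

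The cost is SAP wording and a few extra columns from phases already defined, with no new data collection. The downside is that some events unlikely to be drug-related will appear in the follow-up columns.
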